6.2 Methods of minimising bias

The lymph nodes identified by lymphoscintigraphy will not be marked on the patients, therefore the surgeons won't be influenced when identifying the lymph nodes with ICG and NIRFI. In addition, the surgeon will not have access to the images recorded from lymphoscintigraphy since they are going to be uploaded in the hospital's system only after the surgeon has tried to identify intraoperatively the lymph nodes with ICG.

6.2.1 Randomisation

Not applicable.

6.2.2 Blinding procedures

The surgeons performing SLNB will be the blinded persons. The results of the lymphoscintigraphy will not be marked on the patient's skin as usual and no preoperative access to the images will be granted to the surgeons.

6.2.3 Other methods of minimising bias

In order not to influence the surgeons, the patients are advised not to discuss the lymphoscintigraphy results with them and this will be reinforced during the consent procedure.

6.3 Unblinding Procedures (Code break)

Not applicable.

7. STUDY POPULATION

7.1 Eligibility criteria

Individuals fulfilling all of the following inclusion criteria are eligible for the study:

- Informed consent as documented by signature
- Individual must present with any of the following cancer types:
 - o Malignant melanoma with one of the following characteristics:
 - a. Breslow score ≥ 1 mm

- b. Breslow score ≥ 0.7 mm associated with ulceration
- c. Breslow score ≥ 0.7 mm associated with regression
- d. Breslow score ≥ 0.7 mm associated with Clark Level IV / V
- e. Breslow score ≥ 0.7 mm associated with mitotic rate $\geq 1/\text{mm}^2$ in young patients
- o Merkel cell carcinoma

The presence of any one of the following exclusion criteria will lead to exclusion of the individual:

- age < 18 years
- pregnancy and breastfeeding (pregnancy test to be performed for women of child-bearing potential, defined as women who are not surgically sterilized/hysterectomized, and/ or who are postmenopausal for less than 12 months)
- known allergy to ICG or Iodine
- previous chemotherapy, radiotherapy or surgery to the lymph nodes of interest
- lack of capacity to provide informed consent
- current enrolment in any other interventional study

7.2 Recruitment and screening

Patients who fulfill the inclusion criteria for the study will be sent an information packet detailing the background rationale of the study and the details of the surgical procedure. Prior to surgery a member of the study group will confirm the patient's willingness to participate in the study. If they agree, they will formally consented regarding procedures, risks and benefits of the study.

7.3 Assignment to study groups

Not applicable.

7.4 Criteria for withdrawal / discontinuation of participants

The participants are withdrawn from the study if they withdraw their consent, if the operation cannot take place anymore for medical reasons, if they are proven to have distant metastases following radiological staging or if there are no LNs on lymphoscintigraphy.

8. STUDY INTERVENTION

8.1 Identity of Investigational Products (treatment / medical device)

In all patients of our study a transcutaneous ICG lymphography is performed by injection of ICG intradermally around the scar of the primary excision of the tumour and transcutaneous assessment of fluorescence with the Visionsense™ VS3 – Stereoscopic High Definition Visualisation System (VS3-3DHD).

8.1.1 Experimental Intervention (treatment / medical device)

The Medical device used is the Visionsense™ VS3 – Stereoscopic High Definition Visualisation System (see image). Its use is based on ICG fluorescence visualisation transcutaneously with the device specific Infrared (IR) fluorescence visualisation system. The system is made up of a display and hardware tower and an infrared camera as well as connecting cables.

8.1.2 Control Intervention (standard/routine/comparator treatment / medical device)

Tc 99m based lymphoscintigraphy.

8.1.3 Packaging, Labelling and Supply (re-supply)

Not applicable.

8.1.4 Storage Conditions

Storage according to standard procedures in the facilities of the Plastic Surgery Operation theatre.

8.2 Administration of experimental and control interventions

8.2.1 Experimental Intervention

After induction of anaesthesia, standard procedures for injection of ICG intradermally are performed according to product description and hospital SOPs.

After ICG injection the possible draining lymphatic basins from the primary scar (i.e. axillae, inguinal, popliteal and neck regions) are scanned with the VS3-3DHD camera and all transcutaneous fluorescence spots recorded in the CRF. The scanning is discontinued after a maximum of 15 minutes regardless of findings.

After this the surgeon is unblinded to the results of the lymphoscintigraphy and the further procedures of sentinel lymph node dissections are performed according to surgical intervention standard procedures.

8.2.2 Control Intervention

Tc 99m based lymphoscintigraphy.

8.3 Dose / Device modifications

Not applicable.

8.4 Compliance with study intervention

There is no possibility of non-adherence to the intervention since all study procedures are done once under general anaesthesia after obtaining informed consent.

8.5 Data Collection and Follow-up for withdrawn participants

Should patients choose to retrospectively withdraw their consent to further study participation, all data collected up to the time point of withdrawal will still be analysed in coded form. For withdrawn patients standard follow-up will be pursued.

8.6 Trial specific preventive measures

There are no specific contraindications regarding the use of the VS3-3DHD device.

8.7 Concomitant Interventions (treatments)

There are no specific treatments associated with the use of the medical device.

8.8 Study Drug / Medical Device Accountability

[figure not shown]
Device maintenance plan according to the hospital's technical-medical departments SOP's.

8.9 Return or Destruction of Study Drug / Medical Device

After the study is completed, the VisionSense devices will be returned to the manufacturer.

9. STUDY ASSESSMENTS

9.1 Study flow chart(s) / table of study procedures and assessments

9.2 Assessments of outcomes

9.2.1 Assessment of primary outcome

The primary end-point is determined once the responsible surgeon has either identified or failed to identify a SLN transcutaneously (as per protocol described in chapter 9.3). At this stage the surgeon is unblinded and the results will be compared to the LS findings; all data will be recorded for analysis.

9.2.2 Assessment of secondary outcomes

Secondary outcomes will be made once the study period is completed. Data relating to the ability of SLNs to be successfully identified transcutaneously will be grouped anatomically or according to patient characteristics such as BMI, sex, and age and statistically analysed to determine if certain anatomical regions or patient groups have different sensitivity rates.

9.2.3 Assessment of other outcomes of interest

Not applicable.

9.2.4 Assessment of safety outcomes

Not applicable

9.2.5 Assessments in participants who prematurely stop the study

Any patient whom chooses to terminate the study early will receive the same post-operative (standard) care and follow-up as those included in the study.

9.3 Procedures at each visit

9.3.1.0 Patient booked for sentinel lymph node biopsy.

- Patient identified according to national guidelines that they should be offered a sentinel lymph node (SLN) biopsy
- Patient demographics and skin tumour details checked to ensure they fulfil the inclusion/exclusion criteria of the trial
- Patient information pack sent to home address detailing the study and aims of the clinical trial

9.3.2.1 Patient admission.

9.3.2.1.1 *Informed consent and patient agreement of participation in study*

- Patient admitted to dermatology or plastic surgery ward
- Pre-operative consultation explaining the surgical procedure including the risks and benefits of surgery
- Patient consent to be obtained for both the surgical procedure and for participation in study

9.3.2.1.2 *Pre-operative consultation with anaesthetic department*

- Routine pre-operative assessment
- Routine blood tests as requested by anaesthetic team including pregnancy testing for relevant patients
- Electrocardiogram monitoring where indicated
- **This information will not be recorded for the purpose of this study**

9.3.2.1.3 *Radiological cancer screening (where applicable):*

- Patients will complete radiological cancer screening depending on the type and size of tumour
- This may involve ultrasonography of anatomical lymph node basins for local evidence of regional metastasis or plain chest radiograph with x-ray or computed tomography (CT)
- **This information will not be recorded for the purpose of this study**

9.3.3.0 **Day of surgery.**

9.3.3.0.1 *Nuclear medicine appointment:*

- The patient will attend a nuclear medicine appointment for the lymphoscintigraphy scan (LS) on the morning of the planned surgery
- This will be performed in accordance with the standardised technique of injecting four small volumes (0.1 - 0.4 ml) of Technicium⁹⁹ around the site of the primary tumour
- The patient will then have scans taken at approximately 30 and 120 minutes following injection to locate the SLN(s)
- The patient **will not** have the location of the SLN marked on his or her skin with permanent marker
- The patient will be asked **not to disclose** the location of the detected SLN to the surgeon or any other member of the surgical team to ensure that the surgeon is blinded to the result and limit the degree of bias in the study
- **This information will not be recorded for the purpose of this study**

9.3.3.0.2 *Patient called to the operating room:*

- The patient will be called to the operating room at the time of surgery
- A member of nursing staff will accompany the patient.
- The patient will be anaesthetised under full general anaesthetic

9.3.3.0.3 *Intra-dermal Indocyanine Green (ICG) injection:*

- The responsible surgeon will inject 0.2 – 0.4 ml of ICG intra-dermally around the site of the primary tumour
- The surgeon will wait for a period of 5 – 15 minutes to allow for ICG to be absorbed and passed into the lymphatic system
- After this period, the surgeon will use the VisionSense HD3D camera to attempt to locate the SLN after confirming the camera is functioning correctly by commencing the scan at the site of ICG injection, identified lymph nodes (LN) will be marked with a permanent skin marker in RED.
- The scan will proceed in the following manner depending on the site of the primary tumour:
 - Head and neck tumours:
 - The scan will proceed from the primary tumour to the ipsilateral lymphatic chains to cover the pre-auricular LNs, posterior-

auricular LNs, anterior cervical LNs (Level I – IV) and posterior cervical LNs (Level V)

- The same procedure will be performed on the contra-lateral side
- Trunk and thorax tumour:
 - The scan will proceed from the primary tumour towards the ipsilateral axilla followed by the ipsilateral inguinal region.
 - The same procedure will be performed for the contralateral side
- Upper extremity tumour:
 - The scan will proceed from the primary tumour towards the ipsilateral axilla
 - There is no need to scan other LN basins
- Lower extremity tumour:
 - The scan will proceed from the primary tumour towards the ipsilateral inguinal region.
 - If the tumour is located below or distal to the knee, the popliteal LN basin will be scanned.
 - If the primary tumour is above or proximal to the knee the popliteal LN basin will not be examined

9.3.3.0.4 *Un-blinding of the surgeon to the LS result:*

- The nuclear medicine department will be telephoned and asked to upload the scans and radiology report of the LS onto the electronic PACS system
- The surgeon will visualise the location of the LS scan and locate them on the patient using a gamma probe using a BLUE permanent skin marker
- **The results will be recorded in the CRF**

9.3.3.0.5 *Commencement of the surgical procedure:*

- The surgeon will **ONLY** perform the SLN biopsy on the LNs identified by LS
- Any LNs identified by the VisionSense HD3D camera which do not correlate with the LS results will **NOT** be biopsied
- The operation will be carried out in accordance with the standard operative procedure using a combined approach of gamma probe navigation and fluorescent imaging
- **This information will not be recorded for the purpose of this study**

9.3.3.0.6 *Patient recovery from surgical procedure:*

- Following the surgical procedure, the patient will be woken from general anaesthesia
- The patient will be transferred to the general recovery unit and monitored routinely
- Once the patient vital parameters have been met and their pain controlled, they will be transferred back to the ward
- **This information will not be recorded for the purpose of this study**

9.3.3.0.7 *Post-operative surgical consultation:*

- Once the patient has been re-admitted to the ward the responsible surgeon will make a routine post-operative visit of the patient

- The surgical wounds will be inspected for any early operative complications
- The patient will be informed of the surgical procedure and findings, including the results of the clinical trial
- **Any adverse events will be recorded in the CRF**

9.2.4.0 Post-operative day one

9.3.4.0.1 *Second post-operative consultation:*

- The responsible surgeon will visit the patient on a second occasion the day following surgery
- The surgical wounds will be inspected again to monitor for any early surgical complications
- The patient will have the results of the surgical procedure explained to them for a second time and be asked if they have any questions regarding the procedure or follow up
- **Any adverse events will be recorded in the CRF**

9.3.4.0.2 *Patient discharge:*

- Once the patient has fulfilled standard discharge criteria they will be prepared for discharge
- A prescription for analgesia will be provided

10. SAFETY

10.1 Drug studies

Not applicable.

10.2 Medical Device Category C studies

Not applicable.

10.3 Medical Device Category A studies

10.3.1 Definition and Assessment of safety related events

There are no known patient safety related concerns regarding the use of the device. The device was certified with the CE 0086 marking by the British Standards Institution according to ISO 13485 and adheres to following normatives.

Safety norms:

IEC/EN-60601-1 (2006)

IEC/EN60601-2-18 (2009)

IEC/EN60825-1-2 (2014)

EMI-Norms:

IEC/EN60601-1-2 (2007)

10.3.2 Reporting of Safety related events

Category A study - there is no safety related event reporting necessary.

Reporting to Sponsor-Investigator:

Health hazard that require measures are reported to the Sponsor-Investigator within 24 hours upon becoming aware of the event:

Pregnancies

Reporting is not needed, because pregnancy is an exclusion criteria

Reporting to Authorities:

In Category A studies it is the Investigator's responsibility to report to the local Ethics Committee

- Health hazards that require measures within 2 days

11. STATISTICAL METHODS

This study is a diagnostic sensitivity study designed to analyse the ability of a new diagnostic method in comparison to the current “gold standard” diagnostic procedure. Gold standard diagnostic procedures are the current best-practice for diagnosing a disease. Sensitivity measures inherent validity of a diagnostic test against a gold standard. We want to ensure that the data will yield estimates of sensitivity that have good precision. Study sample size requirements can be calculated based on a clinically acceptable degree of precision, the hypothesized values of sensitivity and the estimated prevalence of disease in the target population.

11.1 Null Hypothesis

We will not do any hypothesis testing. The aim of the study is to determine the sensitivity of VisionSense NIRFI to detect SLNs in comparison to the current gold standard of LS.

11.2 Determination of Sample Size

Sample size at the required absolute precision level for sensitivity can be calculated with Buderer’s formula.⁴ With an expected sensitivity of 60% and assuming a maximum clinically acceptable width of the 95% CI of 10% (i.e. 50 - 70%) we will require 93 LNs identified by LS. All of the patients will have at least one positive LN in LS, but there could also be cases with more than one LN per patient, increasing the precision of the sensitivity estimate. As it is not possible to make a reasonable assumption about the number of LNs per patient and the correlations of the measurements within a patient, we will recruit 93 patients.

11.3 Statistical criteria of termination of trial

Not applicable. This is a diagnostic sensitivity test, we need to examine all the required LNs to determine the sensitivity before deciding whether this method works or not.

11.4 Planned Analyses

11.4.1 Datasets to be analysed, analysis populations

All eligible patients will be included in the analysis.

11.4.2 Primary Analysis

The statistical analysis will be performed by a statistician at the end of the study (i.e., when all patients are included). Baseline characteristics will be reported as mean and standard deviation or median and interquartile range, and number and percentage of patients for continuous and categorical variables, respectively.

The sensitivity (i.e. the proportion of NIRFI and LS positive LN among LS positive LN) will be reported with a 95% confidence interval and adjusted for multiple observations per patients using generalized estimating equations (GEE)¹⁷ or the method by Rao & Scott.¹⁸ The number of LS-negative LN that are NORFI positive will be reported.

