
Result:
	
That the SLN identified by NIRFI is the same as that identified by lymphoscintigraphy.

Study design:
	
A clinical, prospective, single-arm, single-blind, monocentric, diagnostic sensitivity study.

Inclusion and exclusion criteria:
	
Inclusion criteria:
 
- Patient has signed the consent form- Patients who have tumors with any of the following characteristics:
- Malignant melanoma
a) Breslow score ≥ 1 mmb) Breslow score ≥ 0.7 mm with ulcerationc) Breslow score ≥ 0.7 mm with regressiond) Breslow score ≥ 0.7 mm with Clark Level IV/Ve) Breslow score ≥ 0.7 mm with mitosis-rate $\geq 1/\text{mm}^2$ in young patients- Merkel cell carcinoma 
Exclusion criteria:
 
- Age < 18 years- Pregnancy and lactation (perform pregnancy test on women of fertile age [defined as not sterilized, hysterectomized and/or more than 12 months postmenopausal]).- Allergy to ICG and iodine- previous chemotherapy, radiation or surgery of the lymph nodes to be examined- the patient is not able to give his consent to the study- simultaneous participation in other intervention studies
---	--

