4.2 Primary Objective

The study seeks primarily to determine ability of the VisionSense NIRFI technology to transcutaneously identify SLNs as effectively as LS.

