5. STUDY OUTCOMES

5.1 Primary Outcome

Correlation of SLN(s) identified by LS vs. VisionSense NIRFI.

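### The stated outcome is whether NIRFI and LS identify the same nodes, but only sensitivity is estimated with an interval; the reverse direction is left as a bare count

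*Combined protocol and SAP*

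**What the plan says.** The question is worded as agreement in two places. The synopsis gives the result sought as "That the SLN identified by NIRFI is the same as that identified by lymphoscintigraphy", and section 5.1 defines the primary outcome as "Correlation of SLN(s) identified by LS vs. VisionSense NIRFI". Section 4.2 sets the objective of finding whether the camera can "identify SLNs as effectively as LS".

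The statistics section is narrower. Section 11.1 says: "The aim of the study is to determine the sensitivity of VisionSense NIRFI to detect SLNs in comparison to the current gold standard of LS". Section 11.4.2 defines sensitivity as "the proportion of NIRFI and LS positive LN among LS positive LN", with a 95% confidence interval adjusted for several nodes per patient by GEE or the Rao-Scott method. On camera-positive nodes that LS does not show, it adds only: "The number of LS-negative LN that are NORFI positive will be reported" (NORFI is evidently NIRFI). PPV and NPV are in the abbreviation list but in no planned analysis.

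The raw data for the reverse direction will exist: section 8.2.1 has "all transcutaneous fluorescence spots recorded in the CRF". Section 9.3.3.0.5 says that camera-only nodes are not biopsied.

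On patients without an LS node, section 7.4 withdraws participants "if there are no LNs on lymphoscintigraphy", and section 11.5 confines the study to patients with LS-positive nodes. Section 11.4.1 puts every eligible patient in the analysis, and the eligibility criteria in 7.1 do not mention the LS result.

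**The concern.** Agreement between two methods has two sides: how many LS nodes the camera finds, and how many camera-marked nodes are LS nodes. The plan estimates the first with an interval and gives a raw number for the second.

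The second side matters for the use the protocol has in view. The lay summary asks whether the dye can take the place of the radioactive injection, and section 3.7 names less radiation exposure as the long-term aim. A surgeon working from the camera alone would need to know how often a marked node is one that LS would have shown. Because camera-only nodes are not biopsied, comparison with LS is the only check this trial makes on them.

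**Working it through.** **1. The plan's own figure.** Section 11.2 gives an expected sensitivity of 60%, a 95% interval of 50 to 70% (half-width 0.10) and 93 LS-positive nodes. The precision formula is n = z² × p(1 − p) / d².

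n = 1.96² × 0.60 × 0.40 / 0.10² = 92.2, rounded up to 93.

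The figure reproduces. It depends on sensitivity alone, so the sample size sets no precision for the reverse direction.

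**2. Effect of extra marks on sensitivity.** Sensitivity = (nodes positive on both) / (LS-positive nodes). A mark that matches no LS node enters neither term. A mark that matches one can only raise the result. No extra mark can lower it.

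**3. Illustration.** Expected matched nodes: 93 × 0.60 = 55.8, taken as 56. Sensitivity = 56/93 = 60.2% (Wilson 95% CI 50.1 to 69.6%). PPV = 56 / (56 + extra nodes). The documents give no figure for extra nodes, so a range is shown. The intervals are Wilson and ignore clustering.

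| Extra (LS-discordant) nodes | Sensitivity | PPV | 95% CI for PPV |
|---|---|---|---|
| 0 | 60.2% | 100% | 93.6 to 100% |
| 10 | 60.2% | 56/66 = 84.8% | 74.3 to 91.6% |
| 25 | 60.2% | 56/81 = 69.1% | 58.4 to 78.1% |
| 50 | 60.2% | 56/106 = 52.8% | 43.4 to 62.1% |
| 56 | 60.2% | 56/112 = 50.0% | not computed |
| 100 | 60.2% | 56/156 = 35.9% | 28.8 to 43.7% |

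With 10 to 100 extra nodes the PPV intervals span roughly 15 to 20 points, so an informative interval is available at the planned size.

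**4. Patients with no LS node.** The documents give no rate of LS failure. If a share f of patients shows no node, the number withdrawn for 93 retained is 93/(1 − f) − 93. For assumed f of 1%, 2%, 5% and 10% this is 0.9, 1.9, 4.9 and 10.3, or 1, 2, 5 and 11 patients after rounding up. To gauge size only, take 25 other discordant nodes and one camera mark in each withdrawn patient. Pooling those marks would move PPV from 69.1% to:

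- 56/82 = 68.3%
- 56/83 = 67.5%
- 56/86 = 65.1%
- 56/92 = 60.9%

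All four lie inside the 58.4 to 78.1% interval from step 3.

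**The case against.** The strongest reply is that one direction is the declared design. The title and sections 6.1, 11, 11.1 and 11.3 all present a diagnostic sensitivity study, and the agreement wording sits in two loosely phrased lines. This stands to the extent that nothing is wrong with the sensitivity analysis itself. The gap lies between the outcome as worded and the analysis as planned.

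A reader might infer that over-calling by the camera would be hidden or costless. The documents do not support that. The discordant count is to be reported, and together with the number of matched nodes it gives a crude PPV: 56/(56 + 10) needs only those two figures. What is missing is the interval, the allowance for clustering and the spread across patients. Scanning is also limited to prescribed basins (9.3.3.0.3) and to 15 minutes (8.2.1).

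A reader might also infer that the discordant count is too low by design because 7.4 removes patients without an LS node after the camera has been used on them. That is not established. LS is done on the morning of surgery (9.3.3.0.1). The blinding in 6.2.2 and 9.3.3.0.1 covers skin marks, images and node location, and nothing says whether a finding of no node would be passed on before the ICG injection. If it were, there would be no camera marks to lose. If such a patient were scanned, 7.4 does not say that the data are discarded. Section 8.5 addresses data after consent withdrawal only, and 11.4.1 points towards inclusion. The documents are unclear here.

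Finally, a camera-only node need not be an error. It is not biopsied, and where LS shows nothing the reference itself may have failed.

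**Conclusion.** The concern holds as a mismatch between outcome and analysis. The plan asks whether the two methods identify the same nodes, but gives precision for only one direction. At the plan's expected sensitivity, 60% is compatible with a PPV of 85% or 50%, depending on whether there are 10 or 56 extra nodes. That sensitivity does not respond to such nodes is certain. The PPV values rest on assumed counts, and their intervals ignore within-patient correlation.

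The handling of patients without an LS node is a smaller, separate ambiguity between 7.4 and 11.5 on one side and 11.4.1 on the other. It would involve about 2 to 5 patients if LS fails in an assumed 2 to 5%, and only if they are scanned. The addition is worth making because the data are already collected, but it does not invalidate the planned primary estimate.

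**What to change.** In 11.4.2, among patients with at least one LS-positive node, add:

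- PPV: nodes positive on both methods divided by all camera-marked nodes, with a 95% interval by the same GEE or Rao-Scott method. Count nodes, as 11.4.2 already does, not raw fluorescent spots.
- The number of LS-discordant camera nodes per patient.
- The share of patients with at least one such node.

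Call these nodes LS-discordant and not false positive, since they are not biopsied. Node-level specificity should not be attempted, because nodes negative on both methods are not enumerated.

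Reconcile 7.4 and 11.5 with 11.4.1. State that any patient scanned with the camera who proves to have no node on LS leaves both the sensitivity and the PPV analyses, and that the number of such patients and their camera findings are reported separately. Pooling those findings into PPV would confuse failure of the reference with error by the camera.

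The cost is some analysis wording and a few output lines. No procedure, sample size or primary estimate changes. The downside is that the camera's results may look less favourable.
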